9.4.5. HEPATIC FUNCTION ABNORMALITY

Hepatic function abnormality that fulfills the biochemical criteria of a potential Hy's Law case in a study subject, with or without associated clinical manifestations, is required to be reported as "hepatic function abnormal" ***within 24 hours of knowledge of the event*** to the sponsor and AstraZeneca/MedImmune Patient Safety using the designated Safety e-mailbox (see Section 9.2 for contact information, unless a definitive underlying diagnosis for the abnormality (e.g., cholelithiasis or bile duct obstruction) that is unrelated to investigational product has been confirmed.

The criteria for a potential Hy's Law case is Aspartate Aminotransferase (AST) or Alanine Aminotransferase (ALT) $\geq 3x$ Upper Limit of Normal (ULN) together with Total Bilirubin (TBL) $\geq 2x$ ULN at any point during the study following the start of study medication irrespective of an increase in Alkaline Phosphatase (ALP).

- If the definitive underlying diagnosis for the abnormality has been established and is unrelated to investigational product, the decision to continue dosing of the study subject will be based on the clinical judgment of the investigator.
- If no definitive underlying diagnosis for the abnormality is established, dosing of the study subject must be interrupted immediately. Follow-up investigations and inquiries must be initiated by the investigational site without delay.

Each reported event of hepatic function abnormality will be followed by the investigator and evaluated by the sponsor and AstraZeneca/MedImmune.

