		
investigator, in discussion with AstraZeneca Clinical Study Lead.
 
For patients treated with durvalumab in combination with tremelimumab or tremelimumab monotherapy,
 
Permanently discontinue both durvalumab and tremelimumab for
 
1) Grade 3 diarrhea/colitis or 2) Any grade of intestinal perforation
 
Grade 4
 
Permanently discontinue study drug/study regimen.
	
– If perforation is suspected, consult a surgeon experienced in abdominal surgery immediately without any delay.

Hepatitis
 
Infliximab should not be used for management of immune-related hepatitis.
 
 
PLEASE SEE shaded area immediately below this section to find guidance for management of “Hepatitis (elevated LFTS)” in hepatocellular carcinoma (HCC) patients (or secondary tumour involvement of the liver with abnormal baseline values [BLV])
 
	
Any Grade
 
(Refer to NCI CTCAE applicable version in study protocol for defining the CTCAE grade/severity)
	
General Guidance
	
For Any Grade

	
ALT or AST ≤ 3 x ULN or total bilirubin ≤ 1.5 x ULN
	
 • No dose modifications. • If it worsens, then consider holding therapy. 	
– Continue transaminase and total bilirubin monitoring per protocol.

	
ALT or AST $> 3 \leq 5$ x ULN or total bilirubin $> 1.5 \leq 3$ x ULN
	
 – Hold study drug/study regimen dose until ALT or AST ≤ 3 x ULN or total bilirubin ≤ 1.5 x ULN. Resume study drug/study regimen after completion of steroid taper (<10 mg prednisone or equivalent). – Permanently discontinue study drug/study regimen for any case meeting Hy’s law laboratory criteria (AST or ALT $\geq 3 \times$ ULN AND bilirubin $\geq 2 \times$ ULN without initial 	
 – Regular and frequent checking of transaminases and total bilirubin (e.g., every 1 to 2 days) until transaminases and total bilirubin elevations improve or resolve. – If no resolution to ALT or AST ≤ 3 x ULN or total bilirubin ≤ 1.5 x ULN in 1 to 2 days, consider discussing with Clinical Study Lead, as needed. – If event is persistent (>2 to 3 days) or worsens, promptly start prednisone 1 to 2 mg/kg/day PO or IV equivalent.

		findings of cholestasis (i.e., elevated ALP) and in the absence of any alternative cause.	

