	ALT or AST > 5- ≤ 10 x ULN	
 - Hold study drug/study regimen. Resume study drug/study regimen if elevations downgrade to ALT or AST ≤ 3 x ULN or total bilirubin ≤ 1.5 x ULN after completion of steroid taper (<10 mg prednisone, or equivalent). - If in combination with tremelimumab, do not restart tremelimumab. 	
 - Promptly initiate empiric IV methylprednisolone at 1 to 2 mg/kg/day or equivalent. - Perform Hepatology Consult, abdominal workup, and imaging as appropriate. - If still no improvement within 2 to 3 days despite 1 to 2 mg/kg/day methylprednisolone IV or equivalent, promptly start treatment with an additional immunosuppressant.(e.g., mycophenolate mofetil 0.5 – 1 g every 12 hours then taper in consultation with hepatology consult or relevant practice guidelines). Discuss with Clinical Study Lead if mycophenolate is not available. Infliximab should NOT be used.
	Concurrent ALT or AST > 3 x ULN and total bilirubin > 2 x ULN ALT or AST > 10 x ULN OR total bilirubin > 3 x ULN	Permanently discontinue study drug /study regimen.	
 - Promptly initiate empiric IV methylprednisolone at 1 to 2 mg/kg/day or equivalent. - If still no improvement within 2 to 3 days despite 1 to 2 mg/kg/day methylprednisolone IV or equivalent, promptly start treatment with an additional immunosuppressant.(e.g., mycophenolate mofetil 0.5 – 1 g every 12 hours then taper in consultation with hepatology consult or relevant practice guidelines). Discuss with Clinical Study Lead if mycophenolate is not available. Infliximab should NOT be used. - Perform Hepatology Consult, abdominal workup, and imaging as appropriate.
Hepatitis (elevated transaminases and total bilirubin) Infliximab should not be used for management of immune-related hepatitis.	Any Elevations of AST, ALT, or T. Bili as Described Below	General Guidance	For Any Elevations Described 
 - Patients should be thoroughly evaluated to rule out any alternative etiology (e.g., viral hepatitis, disease progression, concomitant medications, worsening of liver cirrhosis [e.g., portal vein thrombosis]). - Monitor and evaluate AST, ALT, ALP, and T. Bili. - For hepatitis B (HBV) + patients: evaluate quantitative HBV viral load, quantitative Hepatitis B surface antigen (HBsAg), or Hepatitis B envelope antigen (HBeAg).

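### With Hy's law liver values and no cause found, section 9.4.5 only interrupts dosing while Appendix A stops it permanently; the two Appendix A hepatitis rows also disagree when ALP is raised

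*Combined protocol and SAP*

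**What the plan says.** Section 9.4.5 defines a potential Hy's law case as AST or ALT at least 3x ULN together with total bilirubin at least 2x ULN, at any time after study drug has started and whatever the ALP. Two dosing consequences follow. If an unrelated diagnosis is established, "the decision to continue dosing of the study subject will be based on the clinical judgment of the investigator". If no diagnosis is established, "dosing of the study subject must be interrupted immediately", and the site is to begin follow-up investigations promptly. The section gives no end point for the interruption and no reference to Appendix A.

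Elsewhere in the protocol body, section 6.2 withdraws a patient when an interruption for drug-related events exceeds 4 consecutive weeks. Section 7.3.1 permits delays, ends treatment at a 4-week delay, and allows restart once the event has recovered to grade 1 or lower or poses no safety risk.

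Two rows of the Appendix A hepatitis table cover the same laboratory picture:

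- **Moderate row** (ALT/AST above 3x and up to 5x ULN, or bilirubin above 1.5x and up to 3x ULN). The default is "Hold study drug/study regimen dose until ALT or AST" or bilirubin falls back to the stated limit, with resumption after the steroid taper. The same cell adds "Permanently discontinue study drug/study regimen for any case meeting Hy’s law laboratory criteria", at 3x and 2x ULN, but only without initial cholestasis (raised ALP) and without an alternative cause.
- **Concurrent row**: "Concurrent ALT or AST > 3 x ULN and total bilirubin > 2 x ULN". The action is permanent discontinuation. The row carries no condition on ALP or on alternative causes.

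**The concern.** These are dosing rules for a serious hepatic signal in a multicenter trial. If two parts of the protocol attach different final actions to the same results, whether a patient is re-exposed to study drug depends on which page the site consults. Patient protection would then not be uniform, and neither would time on treatment or the attribution of discontinuations to toxicity.

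The difference between an interruption and a permanent stop matters here because the protocol body provides a route back to treatment after an interruption.

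**Working it through.** No arithmetic applies to the rules themselves. The check takes each rule literally and applies it to the same laboratory values (all as multiples of ULN).

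Inputs:

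- Section 9.4.5: ALT/AST ≥ 3 and bilirubin ≥ 2, any ALP.
- Moderate row, Hy's law sentence: ALT/AST ≥ 3 and bilirubin ≥ 2, no initial cholestasis, no alternative cause; otherwise hold and resume.
- Concurrent row: ALT/AST > 3 and bilirubin > 2, no further condition.

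| ALT/AST, bilirubin | Cause | ALP | Section 9.4.5 | Moderate row | Concurrent row |
|---|---|---|---|---|---|
| 4, 2.5 | none found | normal | interrupt | permanent stop | permanent stop |
| 4, 2.5 | none found | raised | interrupt | hold, may resume | permanent stop |
| 3, 2 | none found | normal | interrupt | permanent stop | does not apply |
| 3, 2 | none found | raised | interrupt | hold, may resume | does not apply |

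1. **No cause, normal ALP.** Section 9.4.5 interrupts and both Appendix A rows stop permanently. The condition is the same in substance (no diagnosis; no alternative cause), but the stated action differs. A site that follows 9.4.5 with sections 6.2 and 7.3.1 could restart a patient who recovers inside four weeks. A site that follows Appendix A could not.
2. **No cause, raised ALP.** The Hy's law sentence of the moderate row drops out because of the cholestasis condition, leaving hold and resume. The concurrent row still stops permanently. This conflict lies inside Appendix A and does not depend on 9.4.5.
3. **Boundary.** At exactly 3x and 2x ULN, 9.4.5 and the Hy's law sentence apply (at least), but the concurrent row does not (strictly above).
4. **Higher transaminases.** At ALT 6x and bilirubin 2.5x ULN with no cause found, the split is the same, and the row for ALT/AST above 5x and up to 10x ULN adds another hold-and-resume instruction.
5. **Precedence.** Section 7.1 sends sites to Appendix A for infusion reactions. No text ranks Appendix A against 9.4.5 for liver events.

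**The case against.** The strongest reply is that the rules are sequential: interrupt at once while the cause is unknown, investigate, then apply Appendix A. A site that does this complies with both texts, and sections 6.2 and 7.3.1 keep the interruption from being open-ended. This is a reasonable reading, but no text requires it. Section 9.4.5 does not present interruption as a step toward a permanent stop or point to Appendix A for the outcome, and the four-week limits still leave restart open within that time. Nor can the sequential reading settle the raised-ALP conflict between the two Appendix A rows.

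A second reply is that 9.4.5 sits under events requiring reporting, so a broad trigger that ignores ALP can coexist with a narrower stopping criterion. That holds for the 24-hour report: a different ALP condition for reporting alone would be no contradiction. But 9.4.5 attaches a dosing instruction to the same trigger.

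A third reply is that Appendix A calls itself a recommendation whereas 9.4.5 is mandatory. That is a difference in tone; it is not a rule of precedence.

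Two stronger readings are tempting and are not supported:

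- A reader might infer that one patient could be continued, interrupted or permanently stopped, because 9.4.5 allows continuation when an unrelated cause is established and the concurrent row has no exception. However, the Hy's law sentence in the moderate row excludes cases with an alternative cause. The general considerations of Appendix A call for immune-mediated management where no clear alternative etiology exists, and its table for non-immune-mediated reactions requires no dose modification for unrelated events. Together these suggest that a case such as confirmed bile duct obstruction is exempt, in line with 9.4.5. What remains is that the concurrent row does not say so.
- A reader might infer that patients with liver metastases are caught at entry, since inclusion criterion 8B admits AST/ALT up to 5x ULN in them. The same criterion caps bilirubin at 1.5x ULN, so the full definition cannot be met on eligible screening values. Appendix A also routes patients with liver involvement and abnormal baseline values to its own baseline-based table. The remaining gap is that 9.4.5 does not mention that table.

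**Conclusion.** The concern holds for patients who meet the laboratory definition and have no cause established. Section 9.4.5 and Appendix A give different actions, and with raised ALP the two Appendix A rows also differ from each other. For an established unrelated cause, the documents can be read consistently but should say so outright.

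The conclusion rests on a literal reading of each rule and on the absence of any text giving precedence. The size cannot be stated as a rate, because the documents do not give the expected frequency of such events. Against the planned 33 patients, each affected patient is 1/33 = 3.0% of the trial. No effect on the primary response-rate test is shown or claimed. This is a safety-rule inconsistency that should be corrected.

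**What to change.** Reconcile section 9.4.5 with the moderate and concurrent hepatitis rows of Appendix A so that they agree on:

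- the thresholds, including whether values exactly at 3x and 2x ULN count;
- the role of ALP or initial cholestasis;
- the final action when no cause is found, and whether an interruption under 9.4.5 can end in restart under sections 6.2 and 7.3.1.

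State in the concurrent row whether an established unrelated cause is exempt. Add a cross-reference from 9.4.5 to Appendix A, including the baseline-based table for liver involvement, and say which section governs if they differ. The clinical team must decide which action applies in each situation; this review takes no position on that.

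The cost is a wording amendment submitted to the IRB under section 11.6. It adds no procedures, visits or patients.

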9.4.6. PREGNANCY

- **Maternal exposure**

If a patient becomes pregnant during the course of the study, the IPs should be discontinued immediately.

Pregnancy itself is not regarded as an AE unless there is a suspicion that the IP under study may have interfered with the effectiveness of a contraceptive medication. Congenital abnormalities or birth defects and spontaneous miscarriages should be reported and handled as SAEs. Elective abortions without complications should not be handled as AEs. The outcome of all pregnancies (spontaneous miscarriage, elective termination, ectopic pregnancy, normal birth, or congenital abnormality) should be followed up and documented even if the

patient was discontinued from the study.

If any pregnancy occurs in the course of the study, then the Investigator or other site personnel should inform the appropriate AstraZeneca representatives within 1 day, ie, immediately, but **no later than 24 hours** of when he or she becomes aware of it.

The designated AstraZeneca representative will work with the Investigator to ensure that all relevant information is provided to the AstraZeneca Patient Safety data entry site within 1 to 5 calendar days for SAEs and within 30 days for all other pregnancies.

The same timelines apply when outcome information is available.

- **Paternal exposure**

Male patients should refrain from fathering a child or donating sperm during the study and for 90 days after the last dose of durvalumab monotherapy.

Pregnancy of the patient's partner is not considered to be an AE. However, the outcome of all pregnancies (spontaneous miscarriage, elective termination, ectopic pregnancy, normal birth, or congenital abnormality) occurring from the date of the first dose until 90 days after the last dose should, if possible, be followed up and documented.

Where a report of pregnancy is received, prior to obtaining information about the pregnancy, the Investigator must obtain the consent of the patient's partner. Therefore, the local study team should adopt the generic ICF template in line with local procedures and submit it to the relevant Ethics Committees (ECs)/Institutional Review Boards (IRBs) prior to use.

10. STATISTICAL CONSIDERATION

10.1. ANALYSIS SET

10.1.1. EFFICACY ANALYSIS SET

- **Intent-to-Treat Population**

All patients who were screened and were eligible will be included in the intent-to-treat population.

- **Per-Protocol Population**

The per-protocol population excludes patients who did not receive at least one dose study treatment, or who had a major violation of protocol inclusion or exclusion criteria.

10.1.2. SAFETY ANALYSIS SET

Safety analysis set comprises subjects who have been registered and took the study treatment at least once.

10.2. SAMPLE SIZE AND RATIONALE

The primary endpoint is objective response rate of durvalumab in mismatch repair deficient (microsatellite instable) or *POLE* mutated metastatic colorectal cancer patients who have progressed after standard therapies.

Assuming the target of response rate was set to 30% and a rate of 10% or below was considered futile. A 2-stage optimal design, as proposed by Simon, was used to allow early termination of any ineffective treatment early in the study. With a 1-sided, type I error of 5% and power of 0.8, the planned study was to proceed in 2 steps. In the first step, 10 patients were required, and if complete or partial response was observed in 2 or more patients, the study was to proceed to the second step with 19 additional patients (29 patients as a total). If this condition was not met, the study would be stopped for futility. In the second step, if complete or partial response was observed in 6 or more patients, the treatment will be considered effective. Assuming a dropout rate of 10%, 33 patients were required.

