--	---

	
infection must have HBV DNA < 100 IU/mL and must be on antiviral therapy.
 
25. Major surgery or significant traumatic injury within 28 days prior to study treatment.
 
26. Non-healing wound, ulcer, or bone fracture.
 
27. Current evidence of significant gastrointestinal bleeding or (impending) obstruction.
 
28. Concomitant participation in another interventional clinical trial.
 
29. Pregnant or breast-feeding subjects. Women of child-bearing potential must have pregnancy test within 7 days and a negative result must be documented before start of study treatment.
 
30. Substance abuse, medical, psychological or social conditions that may interfere with the subject's participation in the study or evaluation of the study results.

Treatment plan
	
The mismatch repair deficient or microsatellite instable, or POLE mutated metastatic colorectal cancer patients who were refractory to fluoropyrimidines, irinotecan and oxaliplatin with or without targeted agents will be accrued.
 
After checking the eligibility for the study entry, patients will be entered into the study treatment with durvalumab monotherapy.
 
Study treatment consists of durvalumab 1500 mg Q4W for patients > 30 kg, and will be repeated every 4 weeks. For patients ≤ 30 kg, weight based dosing of 20 mg/kg durvalumab Q4W will be used.
 
Response evaluation will be performed every 8 weeks (± 1-week window period). Treatment will be continued until disease progression, unacceptable adverse events or the patient's refusal.
 
Treatment through progression is at the investigator's discretion, and the investigator should ensure that patients do not have any significant, unacceptable, or irreversible toxicity that indicate that continuing treatment will not further benefit the patient. The Investigator should ensure that patients still meet all of the inclusion criteria and none of the exclusion criteria for this study.

Statistical consideration
	
All patients who entered into the study will be included for response rates and survival estimation and who received at least 1 cycle of study treatment will be considered as eligible for safety assessment. Descriptive statistics were reported as proportions and medians. Progression-free survival (PFS) and overall survival (OS) were assessed by the Kaplan-Meier method and the 95% confidence interval (95% CI) for the median time to event was computed.

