연구 목표	
 ✓ 일차 목표 
 • 종양 반응율 (RECIST 1.1 기준) ✓ 이차 목표 
 • irRECIST 에 의한 종양 반응율 • 종양 조절율 (disease control rates) • 무진행 생존 기간 (progression-free survival) • 전체 생존 기간 (overall survival) • 안전성 및 독성 평가 • 탐색적 생체 표지자 연구 
 - Opal Multiplex Tissue Staining with Opal™ including PD-1 and PD-L1
연구 설계	전향적, 공개, 다기관 2상 연구
연구 배경	
표준 치료에 진행한 전이성 대장암의 후기 치료는 제한되어 있다. 후기 치료로 regorafenib과 TAS-102 임상연구 결과가 일부 생존 기간 향상에 도움이 되는 것으로 보고되었으나 그 효과는 아직 불충분하고 일부 심한 독성도 보고되고 있다.
 
DNA 복구 유전자 결핍 (mismatch repair deficiency, dMMR) 또는 현미부수체불안정 (microsatellite instability-high, MSI-H)는 수술적 절제가 시행된 대장암에서 플루오로피리미딘 기반 화학요법의 효과가 없는 음성 예측인자로 알려져 있으며, 전이성 대장암에서는 그 자체가 나쁜 예후를 반영하는 것으로 되어 있다. 그러나 최근 전이성 대장암에서 dMMR 또는 MSI-H가 pembrolizumab의 치료 예측인자로서 역할을 하는 연구 결과가 발표되었다. dMMR/MSI-H 전이성 대장암에서 pembrolizumab을 이용하여 PD-1을 억제하였을 때 종양 반응율이 40%에 달하였다. 반면 DNA 복구 유전자가 정상적으로 발현되는 경우 (mismatch repair proficiency, pMMR)에는 종양 반응율이 0% 였다. 20주 째에 종양이 진행하지 않은 환자의 비율도 78% 대 11%로 dMMR/MSI-H 대장암에서 높았다.
 
dMMR/MSI-H 전이성 대장암이 pembrolizumab 등 면역치료에 반응하는 이론적인 근거 중 하나는, dMMR/MSI-H 전이성 대장암에서 종양 유전자 돌연변이가 매우 많이 발생한다는 것이다. 유전자 돌연변이가 많은 경우 항원에 대한 노출이 많아지기 때문에 면역치료의 역할이 커진다는 이론이다. 실제로 pembrolizumab에 반응하였던 dMMR/MSI-H 대장암 환자의 유전자 돌연변이 개수를 보았을 때 평균 1782개의 종양 유전자 돌연변이가 발견되었다.
 
POLE 유전자 역시 DNA 복구와 염색체 복제 과정에 관여하는 유전자로 알려져 있으며, POLE 유전자 돌연변이가 있는 경우 다른 종양 유전체 돌연변이가 많이

	
발생하는 것으로 보고되어 있다. 즉, pMMR/MSS 대장암에서 POLE 유전자 돌연변이가 있는 경우 dMMR/MSI-H 대장암과 마찬가지로 종양 유전자 돌연변이가 많이 존재하는 것으로 간주할 수 있으며, 이 역시 면역치료의 좋은 대상이 될 수 있다. 위와 같은 배경으로 표준 치료에 진행한 전이성 대장암 중에서 dMMR/MSI-H 또는 POLE 유전자 돌연변이가 있는 환자에서 durvalumab 단독치료의 2상 연구를 계획하였다.

환자 수
	
본 연구의 일차 목표는 dMMR/MSI-H 또는 POLE 유전자 돌연변이가 있는 전이성 대장암 환자에서 durvalumab 단독 치료를 하였을 때의 종양 반응율이다. 목표 종양 반응율을 30%, 10% 미만의 반응율을 보이는 경우 실패하는 것으로 가정하였을 때, Simon 2-stage optimal design에 의하면 1단계에서 10명의 환자 등재 후 2명 이상에서 종양 반응을 보이는 경우 2단계로 진입하고, 2단계에서 추가적으로 19명의 환자를 등재하게 된다 (type I error 5%, power 0.8). 총 29명의 평가 가능 환자가 필요하고, 10%의 탈락율을 고려할 때 총 33명의 환자가 등재된다.

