10.3. STATISTICAL PARAMETERS AND STATISTICAL ANALYSIS PLAN

Safety analysis will be conducted in the safety analysis set. Safety evaluation will include all patients who receive at least one dose of study drug. The safety analysis is based on the abnormality of laboratory test and clinical adverse events. Considering the percentage of laboratory abnormalities or clinical adverse events, descriptive statistics (or Fisher's exact test, Chi-square test for comparison between parameters) will be used. The primary endpoint, the objective response rates, will be described with percentage (%) and 95% confidence intervals. The survival outcomes, secondary endpoints, will be calculated using Kaplan-Meier method, compared using long-rank test and described with 95% confidence intervals. The disease-control rates will be described with percentage (%) and 95% confidence intervals, and compared using odds ratio and Chi-square tests. The Kaplan-Meier method will be used to estimate progression-free and overall survival curves, and the Cox proportional hazards regression model will be used for multivariate analysis of prognostic factors for survival outcomes.

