10.4. FINAL ANALYSIS

Final analysis will be conducted in all patients for all endpoints at completion of follow-up.

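### The cut of 6 responders was derived for 29 patients, but 33 are accrued, all of them enter the response analysis, and no analysis set is tied to the cut

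*Combined protocol and SAP*

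**What the plan says.** Section 10.2 takes 10% as the futile response rate and 30% as the target, with one-sided type I error of 5% and power of 80%. Ten patients enter the first stage, and two or more responders are needed to continue. Then "the study was to proceed to the second step with 19 additional patients (29 patients as a total"), and "In the second step, if complete or partial response was observed in 6 or more patients, the treatment will be considered effective". The section ends: "Assuming a dropout rate of 10%, 33 patients were required". Section 5.1 sets accrual at 33, and section 6.3 rules out replacing patients withdrawn from treatment.

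On who is analysed, the documents say the following:

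- English synopsis, statistical consideration: "All patients who entered into the study will be included for response rates and survival estimation". The Korean synopsis likewise puts all participants into the response analysis.
- Section 10.4: "Final analysis will be conducted in all patients for all endpoints at completion of follow-up".
- Section 10.1.1 defines an intent-to-treat set (screened and eligible) and a per-protocol set (no undosed patients, no major eligibility violations). It names neither as primary, and neither depends on response being assessable.
- Section 10.3 names a set for safety ("Safety analysis will be conducted in the safety analysis set") but none for response: "The primary endpoint, the objective response rates, will be described with percentage (%) and 95% confidence intervals".
- Korean synopsis, patient number: "총 29명의 평가 가능 환자가 필요하고" (29 evaluable patients are needed). It does not repeat the cut of 6, and evaluable is not defined anywhere.

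**The concern.** A count of responders has known error rates only for a known number of patients. The cut of 6 was chosen for 29. Up to 33 will be treated, and the only populations the text names for response are all patients, so a literal reading counts 6 responders among 33. The other reading counts 6 among 29 evaluable patients. No cut is given for any number other than 29, and nothing says which 29 count if 30 to 33 turn out to be evaluable.

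At stake is the primary verdict. The trial is open-label, so responses are known as they occur. If the denominator is settled late, it can be settled with the result in view. On the all-patient reading the stated 5% and 80% generally do not both hold.

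**Working it through.** **Inputs (section 10.2):** p0 = 0.10, p1 = 0.30; stage 1 n1 = 10, continue if 2 or more respond; N = 29; success if 6 or more respond; 10% dropout; 33 accrued.

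**Formula.** P(success) = sum over x = 2 to 10 of P(X1 = x) × P(X2 ≥ c − x), with X1 binomial on 10 patients, X2 binomial on the remaining N − 10, and c the cut.

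**Step 1: the plan's own figure.** N = 29, c = 6, p = 0.10:

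| x in stage 1 | P(X1 = x) | P(X2 ≥ 6 − x), 19 patients | P(X2 ≥ 6 − x), 23 patients |
|---|---|---|---|
| 2 | 0.1937 | 0.1150 | 0.1927 |
| 3 | 0.0574 | 0.2946 | 0.4080 |
| 4 | 0.0112 | 0.5797 | 0.6849 |
| 5 | 0.0015 | 0.8649 | 0.9114 |
| 6 or more | 0.0001 | 1 | 1 |

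Multiplying the second and third columns and adding gives 0.0223 + 0.0169 + 0.0065 + 0.0013 + 0.0001 = 0.0471. The same sum at p = 0.30 gives power 0.8051. A search over two-stage designs returns exactly this one as Simon optimal, and 29/0.9 = 32.2 rounds up to 33. The plan's arithmetic for 29 is right.

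**Step 2: the same cut on all 33, no loss.** Stage 2 now has 23 patients. The second and fourth columns give 0.0373 + 0.0234 + 0.0077 + 0.0014 + 0.0001 = 0.0699. Power is 0.8333.

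**Step 3: the same cut on all 33, with loss.** Assume lost patients count as non-responders and loss is random at one rate d in both stages, so p becomes p(1 − d). The documents state neither assumption.

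| Loss d | Type I error | Power |
|---|---|---|
| 0 | 6.99% | 83.3% |
| 5% | 5.75% | 80.1% |
| 8% | 5.08% | 77.9% |
| 10% (planned) | 4.65% | 76.3% |

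Type I error is at or below 5% only from d = 8.35%. Power is at or above 80% only up to d = 5.1%. The ranges do not overlap.

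**Step 4: loss only among the 23 stage-2 patients.** Both targets are met when 15.3% to 17.8% of the 23 are lost, which is 10.7% to 12.4% of 33. At the planned 10% of 33 (3.3 of 23, or 14.3%), type I error is 5.1% and power 80.9%.

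**Step 5: responders counted among evaluable patients only, cut 6, 10 evaluable in stage 1.** With 30 to 33 evaluable, type I error is 5.3% to 7.0%. With 28, power is 79.3%. Only 29 meets both.

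**Step 6: how often the verdict changes.** If all 33 are evaluable, the first 29 fail and all 33 pass in 2.3% of trials at p = 0.10 and 2.8% at p = 0.30. Exactly 6 responders among 33, with stage 1 passed, occurs in 3.9% and 3.2% of trials. Given that result, the chance that at least one responder is among the last four patients is 50.5% whatever the response rate, and the two counts then disagree.

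**The case against.** The best defence is that 29 is what the plan means. The second stage is defined as 29 in total, the cut is stated for that stage, and the Korean synopsis calls the 29 evaluable and explains 33 as an allowance for dropout. Adding patients up front is also how a no-replacement plan protects its 29. The all-patient sentences can be read as describing estimation, since section 10.3 speaks only of a percentage and an interval.

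Much of this stands: 29 is the natural denominator. It does not give a rule that can be carried out. Evaluable is undefined, the Korean synopsis that uses the word also puts every participant into the response analysis, section 10.4 covers all endpoints, and no text selects 29 patients when more are evaluable.

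Two further points are fair. The size depends on assumed loss: the 7.0% needs no loss at all, at the planned 10% under equal random loss only power is missed, and with that loss confined to stage 2 the rule is almost on target. The practical effect is also small overall, because the near-even chance of disagreement applies only to a result seen in 3% to 4% of trials. These points limit the severity but leave the gap open.

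**Conclusion.** The concern holds. The design is correct for 29 patients, and the inflation to 33 is correct. The fault is that the decision rule has no stated denominator, while the text sends all patients into the response analysis.

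On 29 evaluable patients the stated error rates hold (4.7% and 80.5%). On all 33 with the same cut, type I error reaches 7.0% with no loss, and power falls to 76.3% at the planned 10% loss. No common random loss rate meets both targets when losses count as non-response; the exception found with 10 patients in stage 1 is a narrow band of loss confined to stage 2. This should be fixed, but it does not undermine the design: the verdict would differ in 2.3% to 2.8% of trials if all 33 are evaluable.

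**What to change.** In sections 10.1 and 10.2 and both synopses, before the final response count is tabulated:

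- State that the rule applies to the first 29 response-evaluable patients in order of enrolment (first 10 evaluable for stage 1), with 6 or more responders required. Keep the cut at 6 if fewer than 29 are evaluable.
- Define evaluable in section 10.1 without reference to outcome, and count death or progression before the first scan as non-response.
- Report the response rate in all entered patients as an estimate with its 95% confidence interval.
- Because the trial is open-label, record the date of the change and which response data had been seen by then.

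The cost is wording only, with no extra patients. Up to 4 treated patients would not count toward the decision, though they stay in the reported rate. With 10% random loss independent of response (assumed), the chance of at least 29 evaluable among 33 is 77%. Averaged over that loss, type I error is 4.5% and power 79.96%. With 25 to 28 evaluable, type I error is 2.8% to 4.2% and power 74.0% to 79.3%.

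If the sponsor prefers to count all entered patients, the cut should be 7 or more of 33 (type I error 3.1%, power 80.1% with no loss). A cut of 6 holds 5% there only if enough patients are lost, from about 8.4% under equal random loss. The plan should then state that, with a cut of 7, power is about 71% at 10% loss, and 75.9% to 79.0% if only 30 to 32 are enrolled.
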